Limited data are available regarding the pharmacokinetics of DEBIRI. Previous studies have shown a better toxicity profile compared to systemic irinotecan, with the main adverse event of post embolization syndrome (45). Recent data from Martin et al. reported some pharmacokinetics of the drug showing only minimally detectable levels of plasma irinotecan and its active metabolite SN-38 after up to 3 DEBIRI treatments in chemotherapy naïve patients with hepatic metastases from colorectal cancer. Each DEBIRI treatment involved administration of 100mg irinotecan loaded onto 100-300 μ m beads and delivered via the hepatic artery (49). Our previous experience demonstrated increased alkaline phosphatase with use of the 100mg dose of DEBIRI among heavily treated patients. It is possible that this patient population is less amenable to intrahepatic therapy. Alternatively the use of larger bead size may contribute to the poor tolerance. Since refractory patients are often referred for these treatments due to limited treatment options, it is important to identify the MTD for this drug in this patient population. In the proposed phase I study we will use a smaller bead size and carefully escalate the irinotecan dose. These smaller beads are thought to result in better tumor penetration and drug delivery with less embolic effect. We will initiate treatment at 50mg of DEBIRI and escalate by 25mg with every subsequent treatment cohort until the MTD is reached. Cohort expansion will be planned at the MTD. Data from this trial will be used for development of future clinical trials utilizing DEBIRI among patients with refractory disease.

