3.0 Patient selection

3.1 Inclusion

3.1.1 Patients must be 18 years or older.

3.1.2 Patients must have a histologically or cytologically confirmed adenocarcinoma of the colon or rectum that is metastatic to the liver and unresectable and for which standard curative measures do not exist or are no longer effective.

3.1.3 Patients must have received prior fluoropyrimidine, oxaliplatin and irinotecan-based therapy for their disease and had progression or intolerance to these agents that resulted in treatment discontinuation.

3.1.4 Liver disease must not be amenable to potentially curative surgical resection.

3.1.5 Patients must have liver-only or liver-predominant disease to be eligible for this study. Liver predominant disease is defined dominant metastatic burden in the liver, with extra-hepatic disease that is judged by the investigator as unlikely to be life threatening within 3 months.

3.1.6 Patients must have a patent portal vein as documented by CT, MRI, or ultrasound.

3.1.7 Prior radiation therapy is allowed but must have been completed ≥ 4 weeks prior to study entry. Patients with history of prior radiation to the liver including radio-labeled microspheres cannot take part in this study.

3.1.8 Eastern Cooperative Oncology Group performance status 0 or 1.

3.1.9 Previous surgery or RFA to the liver is allowed. Patients with history of chemoembolization or radio-labeled microspheres are excluded.

3.1.10 Life expectancy of ≥ 12 weeks.

3.1.11 Patients must have organ and marrow function as defined below:

Leukocytes	$\geq 3,000/\mu\text{L}$
Absolute Neutrophil Count	$\geq 1,500/\mu\text{L}$
Platelets	$\geq 100,000/\mu\text{L}$
Total Bilirubin	$\leq 1.5 \times \text{ULN}$
AST(SGOT)/ALT(SGPT)	$\leq 2 \times \text{ULN}$
Alkaline Phosphatase	$\leq 2 \times \text{ULN}$
Creatinine	$\leq 2.0 \times \text{mg/dL}$
PT/PTT	$\leq 1.5 \times \text{ULN}$

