4.0 Treatment plan

This will be a single-center phase I study of DEBIRI for the treatment of metastatic colorectal cancer with liver only or liver predominant metastases. Treatment will be given in the interventional radiology department. All patients will be hospitalized for observation following DEBIRI treatment. Reported adverse events and potential risks of these agents and appropriate dose modifications are described in Section 5.0. No investigational or commercial agents or therapies other than those described below may be administered with the intent to treat the patient's malignancy.

The following criteria for recovery of all toxicities must be documented prior to any additional DEBIRI treatments.

- Non-hematologic toxicities related to prior DEBIRI therapy must recover to \leq grade 1 prior to any additional treatment.
- Alkaline phosphatase/ AST/ALT level must recover to \leq grade 1 (less than 2.5 the upper limit of normal).
- Bilirubin elevation must recover to \leq grade 1 (less than 1.5 the upper limit of normal)
- Neutropenia and thrombocytopenia must recover to \leq grade 1 prior to any additional treatment

4.1 DEBIRI dose:

This will be a typical phase I study design of 3+3. The first cohort of patients will receive a dose of 50 mg of irinotecan per DEBIRI treatment. We will escalate by 25 mg with subsequent cohorts up to a dose of 100 mg of irinotecan per DEBIRI treatment (section 4.3).

Table 2: Dose Escalation Schedule

Dose Level	Dose of Irinotecan in beads
Level 1	50 mg per dose
Level 2	75 mg per dose
Level 3	100 mg per dose

At each dose level patients will be treated based on the presence of unilobar or bilobar disease and treated as described below.

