4.1.2 Patients with bi-lobar disease

At each dose level the dominant lobe will be treated with the appropriate dose of DEBIRI for two treatments 3 weeks apart. CT images of the liver will be used to determine which lobe has the highest number or the largest lesions, and will be considered the dominant lobe. The response will be evaluated with CT at 8 weeks. In the absence of evidence of progression in the treated lobe (dominant lobe), 2 additional treatments can be administered to the untreated (non-dominant) lobe, at the same dose level. Repeat CT scan will be performed at 16 weeks. Further treatment is at the discretion of the treating physician.

- Treatment considerations
- Prior to each subsequent therapy patients will have all their blood work reviewed, to assure that they fill the eligibility criteria set forth for the study in section 3.1.11.
- Treatment may be delayed up to 2 additional weeks for labs to recover
- Failure to recover after 2 additional weeks will result in patient removal from the study
- Evaluating Response
- For purposes of planning follow-up treatments and measuring response, response will be defined by RECIST criteria for the treated lobe only.

- Progression of extra-hepatic metastases or progression in the untreated lobe will not be considered progression for the purposes of this trial. However, in these cases the patient and his treating physician may elect to terminate participation in this study.
- Response rate in treated liver lesion will be classified using RECIST criteria as outlined in section 8.0.

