4.3 Definition of Dose-Limiting Toxicities

Definition: This will be defined as any of the following toxicities occurring during the 3 weeks following each DEBIRI treatment that are judged as possibly, probably, or definitely related to study agent:

- \geq Grade 3 non-hematologic toxicity (excluding nausea, vomiting, or diarrhea responding to symptomatic management or LFTs)

- \geq Grade 3 nausea, vomiting and diarrhea that has not responded to maximal medical symptomatic management after \geq 72hr will be considered a DLT
- Grade 3 thrombocytopenia lasting > 5 days
- Grade 3 thrombocytopenia with \geq grade 3 bleeding at any site
- Grade 4 thrombocytopenia
- Grade 4 neutropenia lasting > 5 days or associated with fever or infection
- Grade 3 alkaline phosphatase increase lasting more than 2 weeks post procedure
- Grade 4 alkaline phosphatase at any time
- Grade 3 ALT, AST and/or bilirubin elevation will be classified as a DLT based on the following criteria:
 - persistent AST/ALT elevation of 5-10 times the upper limit of normal for more than 2 weeks
 - Persistent AST/ALT elevation of $>10-20$ times the upper limit of normal for more than 1 week
- Grade 4 ALT, AST and/or bilirubin elevation at any time.

Dose escalation will proceed to the next cohort according to the following schema:

# of Patients with DLT at a Given Dose	Escalation Decision Rule
0 out of 3	Enter 3 patients at the next dose level.
≥ 2	Dose escalation will be stopped. This dose level will be declared to have exceeded the maximum tolerated dose. Three additional patients will be entered at the next lowest dose level if only 3 patients were treated previously at that dose.
1 out of 3	Enter at least 3 more patients at this dose level. 
 • If 0 of these 3 patients experience DLT, proceed to the next dose level. • If 1 or more of this group suffer DLT, then dose escalation is stopped, and this dose is declared to have exceeded the maximum tolerated dose. Three additional patients will be entered at the next lowest dose level if only 3 patients were treated previously at that dose.
≤ 1 out of 6	This is generally the MTD and recommended phase 2 dose. At least 6 patients must be entered at the recommended phase 2 dose.

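### Removal for laboratory values that have not recovered is not in itself a DLT, and the permitted delay falls in no DLT window, so some treatment-limiting toxicity cannot reach the escalation rule

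*Combined protocol and SAP*

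**What the plan says.** The course under test is two treatments of a lobe, 3 weeks apart (sections 4.1.1 and 4.1.2). Under the treatment considerations in section 4.1.2, blood work is reviewed before each further treatment "to assure that they fill the eligibility criteria set forth for the study in section 3.1.11". That section sets alkaline phosphatase and AST/ALT at no more than 2 x ULN and platelets at no less than 100,000. Section 4.0 gives a different condition for retreatment: alkaline phosphatase and AST/ALT at "grade 1 (less than 2.5 the upper limit of normal", with neutrophils and platelets also back to Grade 1 or better.

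If the values are not met, "Treatment may be delayed up to 2 additional weeks for labs to recover". After that, "Failure to recover after 2 additional weeks will result in patient removal from the study".

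Section 4.3 defines a DLT as "any of the following toxicities occurring during the 3 weeks following each DEBIRI treatment", provided it is at least possibly related to the study agent. Some listed items concern persistence, for example "Grade 3 alkaline phosphatase increase lasting more than 2 weeks post procedure". None concerns a delayed treatment, non-recovery at the time of retreatment, or removal.

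Section 9.0 makes a patient evaluable for DLT after at least one full cycle, a term that is not defined. It gives no rule for replacing patients.

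**The concern.** The maximum tolerated dose is the primary objective, and the escalation table and the expansion stopping rule see only listed DLTs. A patient can be unable to receive the second treatment because of related toxicity, be removed at about week 5, and contribute no DLT. If this happened often at a dose, that dose could still be escalated past, or be declared the MTD and expanded, although many patients could not complete the course. Liver tests are where the protocol itself sees a problem. Section 1.5 says: "Our previous experience demonstrated increased alkaline phosphatase with use of the 100mg dose of DEBIRI among heavily treated patients", and 100 mg is the top level here.

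**Working it through.** **Timing.** Treatment 1 is on Day 1 and treatment 2 is planned for Day 22, when the first 3-week window closes. The latest permitted treatment 2 is Day 22 + 14 = Day 36 (each ±2 days). A second window opens only if treatment 2 is given. About Days 22 to 36 therefore belong to no window for a delayed patient. The Grade 4 liver-test items say they apply at any time, but they sit under the 3-week definition.

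**What is and is not counted under section 4.3.**

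| Finding that blocks treatment 2 | Listed DLT? |
|---|---|
| Grade 3 alkaline phosphatase for more than 2 weeks | Yes |
| AST/ALT 5-10 x ULN for more than 2 weeks, or >10-20 x ULN for more than 1 week | Yes |
| Grade 3 thrombocytopenia for more than 5 days; Grade 4 thrombocytopenia | Yes |
| Grade 4 alkaline phosphatase, AST/ALT or bilirubin | Yes |
| AST/ALT above the retreatment limit but below 5 x ULN | No |
| Alkaline phosphatase above the limit but below Grade 3 | No |
| Grade 2 thrombocytopenia | No |
| Grade 3 neutropenia | No |
| Grade 3 bilirubin | No: it is named, but both sub-criteria concern AST/ALT, and the general Grade 3 item excludes liver tests |
| Onset after Day 21 | No: outside the window |

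**Evaluability.** If a full cycle is one treatment, the removed patient counts as a non-DLT. If it is the two-treatment course, the patient leaves the denominator. Neither reading scores a DLT. The figures below use the one-treatment reading.

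**The plan's own figures.** Section 9.0 gives about 9% and 85% for stopping the expansion at true DLT rates of 10% and 33%. Take 14 expansion patients, a stop at 4 DLTs in total, and at most 1 DLT among the 6 MTD patients:

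[P(X6=0) × P(X14≥4) + P(X6=1) × P(X14≥3)] / P(X6≤1)

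- At 10%: (0.5314 × 0.0441 + 0.3543 × 0.1584) / 0.8857 = 0.090.
- At 33%: (0.0905 × 0.7301 + 0.2673 × 0.8899) / 0.3578 = 0.850.

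Both reproduce.

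**Escalation.** From the table in section 4.3, with p the chance that a patient scores a DLT:

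P(escalate) = (1−p)³ + 3p(1−p)² × (1−p)³

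Let d be the listed-DLT rate and q the chance that a patient without a listed DLT is removed for related non-recovery. The documents give no q, so it is an assumed range. As written, p = d. If removals counted, p = d + (1−d)q.

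| d | q | p if counted | As written | If counted |
|---|---|---|---|---|
| 0 | 10% | 0.10 | 1.00 | 0.729 + 0.243 × 0.729 = 0.91 |
| 0 | 20% | 0.20 | 1.00 | 0.512 + 0.384 × 0.512 = 0.71 |
| 0 | 30% | 0.30 | 1.00 | 0.343 + 0.441 × 0.343 = 0.49 |
| 0 | 40% | 0.40 | 1.00 | 0.216 + 0.432 × 0.216 = 0.31 |
| 10% | 10% | 0.19 | 0.91 | 0.531 + 0.374 × 0.531 = 0.73 |
| 10% | 20% | 0.28 | 0.91 | 0.373 + 0.435 × 0.373 = 0.54 |

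**Effect on the expansion rule.** With d = 10% and q = 10%, the stopping formula at p = 0.19 gives 0.41, against 0.09 as written.

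**The case against.** The strongest reply is that section 4.3 sets its own liver-test thresholds, with grade and duration, and so has already chosen which non-recovery is dose-limiting. That stands for the items listed. A reader might infer that toxicity which fails to recover is never a DLT, and the list does not support that. The reply does not cover Grade 3 bilirubin, which is named without a criterion that can be met, or the days after the window closes.

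Second, q may be small. Section 1.3 describes a randomised phase III trial in which 58% of patients had liver tests above 3 x ULN, yet all values normalised after 3 weeks and no treatment was delayed. That is another trial and does not fix q here, but it weighs against assuming a large value. A reader might also infer that the protocol describes liver tests as slow to recover. The available text says only that alkaline phosphatase rose, and section 1.4 notes that the three patients with significant elevation had progressive disease, which may have contributed.

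Third, counting every removal would go too far. The removal rule is not limited to related changes, and the two retreatment limits differ. Values between 2.0 and 2.5 x ULN pass section 4.0 but fail section 3.1.11, so a blanket item could turn them into DLTs. This stands, and it is why the scoring has to be settled together with the limits.

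Fourth, the rule is printed under bi-lobar disease, so its reach to unilobar patients is by implication. Toxicity is also recorded until study completion (section 9.1.1). Both are true, but recording an event does not bring it into the DLT count.

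**Conclusion.** The gap is real and bears on the primary endpoint, but it is narrower than the removal rule alone suggests. It covers at least possibly related non-recovery that meets no listed item: lower-grade values above the retreatment limit, Grade 3 bilirubin, Grade 3 neutropenia, and onset after Day 21. A cohort with such patients can fail to receive treatment 2 and still score no DLT.

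The size depends on q, which is assumed, and on the one-treatment reading of a full cycle. At q = 10% the effect on escalation is modest when there are no listed DLTs. It grows quickly with q, and with a listed-DLT rate above zero. A reader might infer that escalation is certain whatever q is, but that needs a listed-DLT rate of exactly zero. At 100 mg there is no higher level, so what is at stake there is the MTD declaration and the expansion. The plan's 9% and 85% are correct for DLTs as now defined.

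**What to change.** By amendment:

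- State in section 4.3 that for a delayed patient the DLT observation period runs to the next treatment or to removal.
- Reconcile sections 3.1.11, 4.0, 4.1.2, 4.3 and 9.0, so that the plan says how a patient removed for at least possibly related non-recovery enters the DLT count and the denominator, which retreatment limit applies, whether the removal rule covers unilobar patients, and what a full cycle is.
- State the criterion intended for Grade 3 bilirubin.

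The clinical thresholds and the length of the delay stay with the sponsor.

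No new data are needed, because the study calendar already requires weekly blood counts and chemistry. The cost is that a delayed patient's DLT status is final up to 2 weeks later, which can hold up a cohort decision. If the DLT definition widens to include removals, the stopping chances in section 9.0 no longer describe the rule and must be recalculated, as the rise from 9% to about 41% at d = q = 10% shows.

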4.6 Duration of therapy

Therapy will continue per protocol until any of the following conditions occur

- Disease progression in treated lobe.
- Intercurrent illness that prevents further administration of treatment.
- Unacceptable adverse events.
- Patient decides to withdraw from study.
- General or specific changes in the patient's condition which render the patient unacceptable for further treatment in the judgment of the investigator.
- Judgment of the treating physician that further therapy is unlikely to be of benefit to the patient

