7.0 Study Calendar

All pre-study/baseline evaluations except serum pregnancy test may be performed up to 28 days prior to registration. A timetable of relevant assessments is provided in the table below for uni-lobar and bi-lobar disease (all tests can be performed within ± 2 days of this schedule). This timetable contains the schedule for two treatments 3 weeks apart followed by CT on week 8. The schedule can be repeated for additional treatment in appropriate cases (section 4.2.1).

Based on experience from previous studies using DEBIRI there exists a risk of post procedure transient edema, which may confound the response evaluation by RECIST criteria. In case of disease progression on week 8 imaging the patient will be followed with repeat CT at 12 weeks to rule out the possibility of edema accounting for the progressive disease.

Study Calendar

	Pre-Study	Day 1 (± 2) ⁱ	Day 2 ⁱ	Day 8	Day 15	Day 22 (± 2) ⁱ	Day 23 ⁱ	Day 29	Day 36	Day 57	EOT ^h	Follow Up for Survival ^j
Planned treatment (Unilobar/dominant lesion in bilobar disease) ± 2 days ^a		X				X						
Informed consent	X											
Demographics	X											
Medical History ^b	X											
Concurrent meds	X	X-----X										
Physical exam ^b	X		X	X	X	X	X	X	X		X	
Height	X											
Performance Status	X					X					X	
CBC w/diff ^c	X		X	X	X	X	X	X	X		X	
Serum chemistry ^c	X		X	X	X	X	X	X	X		X	
CEA ^d	X									X	X	
PT/INR/PTT ^e	X					X					X	
Adverse Event Evaluations		X-----X										
CT scan of the chest abdomen & pelvis ^f	X									X ^K		
B-HCG ^g	X											
Hepatic angiogram		X										

a. Patients with unilobar disease will be treated on day 1 ± 2 days and 3 weeks later on day 22 ± 2 days with CT 8 weeks after the initial treatment. Patient with bilobar disease will receive treatment to the dominant lobe on day 1 ± 2 days and 3 weeks later on day 21 ± 2 days with CT 8 weeks after the initial treatment. Patients without evidence of progression will be candidates for treatment of the non-treated lobe for 2 treatments 3 weeks apart.
b. Medical history and physical examination will be obtained prior to each treatment according to the treatment schedule (± 2 days). Pre-treatment medical history can consist of interval history.
c. CBC and Chemistry are to be obtained on the day before treatment (± 2 days), and every week while on the study (± 2 days). Additional blood tests should be performed per the discretion of the treating physician. Blood work obtained within ± 2 days may be used.

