d. CEA evaluation will be obtained at the beginning of the study and with each imaging evaluation.
e. PT/INR/PTT only required prior to each procedure.
f. Additional imaging may be obtained at discretion of treating physician (e.g. MRI, PET scan, etc.). Alternative imaging of liver (ie MRI in place of CT scan) is acceptable when preferred by treating physician. MRI of the liver may be used as a substitute for a CT scan for patients with creatinine 1.5-2.0 who are at risk for contrast induced nephropathy. Diabetic patients treated with medications from the biguanides family such as Metformin would be required to hold their medicine for 1 day before and 2 days after their scheduled CT scan.
g. Serum pregnancy test (women of childbearing potential) within 72 hours before treatment.
h. Off-study evaluation. Two consecutive measurements taken at least 4 weeks apart must be used to document partial or complete responses in patients meeting these criteria with measurable disease. Follow-up details are available in section 4.7.
i. Following the procedure the patient will be admitted for overnight observation. On day 1 post treatment blood work including CBC and CMP will be obtained along with physical examination.
j. Patients will be followed up for overall survival status. Medical evaluation is NOT required to determine status. The patient will be clinically evaluated approximately 30 days after completion of the trial. Telephone follow up at 3 month intervals for up to 2 years for survival and toxicity monitoring will be conducted. At treating physician discretion, patients may be followed more frequently for toxicities felt to be treatment-related.
k. Patients who demonstrate progression with their Day 57 (week 8) CT scan should have a repeat CT scan at week 12 to rule out inflammation as a source of tumor enlargement.

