8.0 Measurement of Effect

Although response is not the primary endpoint of this trial, patients with measurable disease will be assessed by standard criteria. For the purposes of this study, all patients will be evaluated for response 8 weeks following the administration of DEBIRI, response rate will be calculated based on the treated lobe only. In addition to a baseline scan, confirmatory scans must be obtained at least 4 weeks following the initial documentation of complete or partial response. In cases of disease progression at 8 weeks, repeat CT will be done at 12 weeks to exclude the possibility of treatment related transient edema accounting for disease progression.

Definitions

Response and progression will be evaluated in this study using the international criteria proposed by the Response Evaluation Criteria in Solid Tumors (RECIST) Committee version 1.1 (50, 51) . RECIST 1.1 limits the number of measurable lesions in an organ to 2 and the total number of measurable lesions to 5. Since response is being evaluated in this study only in the treated lobe of the liver, we will measure response on up to 5 total lesions in that lobe of liver.

Patients must have at least one measurable lesion, defined as >20mm using CT or MRI, or >10mm using spiral CT. Where disease is restricted to a solitary lesion, its neoplastic nature must be confirmed by cytology/histology.

Baseline measurements must be taken not more than four weeks prior to commencement of treatment. The same measurement technique (CT/MRI) must be used at baseline and follow up. No more than 5 target lesions in the liver will be identified. Those with the largest diameters should be included.

A sum of the longest dimension (LD) for all target lesions will be calculated and reported as the baseline sum LD. The baseline sum LD will be used as reference to further characterize the objective tumor response of the measurable dimension of the disease. Change on the sum of these dimensions affords some estimate of change in tumor size and hence therapeutic efficacy.

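### The lab-recovery rule in 4.1.2 takes a patient off study at about Day 33-38, before the Day 57 CT, and no scan is scheduled after removal, which conflicts with 8.0 and 9.1.2

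*Combined protocol and SAP*

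**What the plan says.** Under the treatment considerations in 4.1.2, labs must meet the 3.1.11 limits before each further treatment, and treatment may be delayed by up to two weeks. After that: "Failure to recover after 2 additional weeks will result in patient removal from the study".

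The calendar in 7.0 puts treatment 2 on Day 22 ± 2. For bilobar disease, footnote a has treatment 2 "3 weeks later on day 21 ± 2 days with CT 8 weeks after the initial treatment". The CT row is marked at pre-study and Day 57 only, with a week-12 repeat if Day 57 shows progression. Section 4.1.2 adds a week-16 CT for bilobar patients whose second lobe is treated. The end-of-treatment and follow-up columns have no CT. Section 4.7 gives one clinical visit at about 30 days and then telephone contact. Section 4.6.1, on withdrawal, keeps no scan.

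On response, 8.0 says that "all patients will be evaluated for response 8 weeks following the administration of DEBIRI". Section 9.1.2 keeps every patient with measurable disease in the response assessment, whatever the treatment deviations and even if ineligible. It also provides an unknown category for patients who cannot be assessed.

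**The concern.** The rule acts before any response scan has been taken. A coordinator who follows 4.1.2 and the calendar has no Day 57 CT to order for a patient who is already off study. That patient would usually end up inevaluable under 8.1.1, or unknown under 9.1.2, and would have no scheduled scan for progression in the treated lobe. Response and time to progression are both secondary objectives.

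The loss would not be random with respect to toxicity, because failed lab recovery after DEBIRI is what triggers it. Nor is the trigger obviously remote. The 3.1.11 limits for alkaline phosphatase and AST/ALT (2 × ULN) are tighter than the recovery criterion in 4.0 (below 2.5 × ULN), so persistent values below DLT level could lead to removal. Raised alkaline phosphatase at 100 mg in heavily treated patients is also one of the reasons that 1.5 gives for running this trial.

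**Working it through.** **Inputs.** Treatment 2 on Day 22 ± 2 (calendar) or Day 21 ± 2 (footnote a, bilobar); maximum delay 14 days (4.1.2); CT at week 8, shown as Day 57 (7.0); test window ± 2 days (7.0); accrual 9-30, with 6 patients at the MTD plus 14 in expansion (9.0).

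**The plan's own dates.** Three weeks after Day 1 is 1 + 21 = Day 22. Eight weeks after Day 1 is 1 + 56 = Day 57. Both agree with the calendar; the Day 21 in footnote a is one day off it.

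**Removal day = treatment 2 day + 14.**
- Calendar: 20 + 14 = 34 to 24 + 14 = 38, so Day 34-38.
- Footnote a: 19 + 14 = 33 to 23 + 14 = 37, so Day 33-37.
- Combined: Day 33-38.

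**Gap to the CT.** 57 − 38 = 19 days to 57 − 33 = 24 days. With the CT window of Day 55-59, it is 55 − 38 = 17 to 59 − 33 = 26 days.

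**Scheduled contact after removal.** If removal counts as completion, the 30-day visit falls at 33 + 30 = Day 63 to 38 + 30 = Day 68. It is a clinical evaluation without imaging, and telephone calls follow. The removed patient therefore has no scheduled post-baseline scan. A unilobar patient who completes both treatments has one, plus conditional repeats. Time-to-progression imaging is thus sparse for everyone; the difference is none instead of one.

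**Size.** The documents give no frequency of failed recovery. Each removed patient leaves 1/N of week-8 response status unknown: 1/9 = 11.1%, 1/20 = 5.0%, 1/30 = 3.3%. As an assumed range, one to three such patients would make the interval between the worst-case and best-case response rate 5 to 15 points wide at N = 20 and 3.3 to 10 points wide at N = 30.

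**Endpoints not touched.** The DLT window is three weeks after each treatment (4.3). For treatment 1 it ends at about Day 22, before removal. The sample size and stopping rule in 9.0 use DLTs only. Survival is unaffected if the 4.7 telephone follow-up continues after removal.

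**The case against.** The strongest reply is that the literal reading is not what was meant. The sentence sits under treatment considerations, and the protocol uses study, trial and protocol loosely for treatment. Section 8.1.2 speaks of discontinuing the protocol when liver-directed treatment no longer helps, and 4.6.1 withdraws patients from the study for progression although survival is followed for two years. Sections 8.0 and 9.1.2 both say that everyone is assessed, without exempting patients who stop early. Some calendar footnotes hint at imaging at the off-study visit. CEA is marked there, and footnote d says "CEA evaluation will be obtained at the beginning of the study and with each imaging evaluation". Footnote h, attached to that visit, reads: "Off-study evaluation. Two consecutive measurements taken at least 4 weeks apart must be used to document partial or complete responses". Footnote f allows extra imaging at the physician's discretion.

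Much of this stands. A reader might infer that the protocol has no text supporting a week-8 scan for these patients, or that their scans would certainly be skipped. Sections 8.0 and 9.1.2 rule out the first, and the ambiguity rules out the second. But those sections state an intent and schedule no scan for someone off study, and footnote f permits a scan without requiring one. Where the protocol means the end of treatment it can say so, as in 4.6: "Therapy will continue per protocol until any of the following conditions occur".

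The second reply is that few patients may be affected. In the phase III study described in 1.3, liver values normalized in time for the next treatment and there were no delays. This also stands, although 1.4 voices concern about tolerability in the heavily pre-treated patients enrolled here.

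**Conclusion.** The point holds as an inconsistency in the text with a specific consequence. Followed as written, 4.1.2 and the calendar leave a toxicity-triggered gap in week-8 response and treated-lobe time to progression, which 8.0 and 9.1.2 do not intend. Removal at Day 33-38 (Day 34-38 by the calendar alone) and the 19-24 day gap follow directly from the stated days. The number of patients affected is unknown, and the effect on time to progression cannot be quantified from the documents.

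Two stronger inferences are not supported:
- **An inflated response rate.** Section 9.1.2 gives patients without a scan a category. If they stay in the denominator, the rate is at most 1/N too low for each removed patient who would have responded.
- **Removed patients are more likely to be progressing.** Section 1.4 reports progression in three patients with marked alkaline phosphatase elevation, but it also offers a post-procedural cause. The available text does not show their denominator or timing.

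The conclusion assumes that the rule, printed under the bilobar heading, also applies to unilobar patients. Bilobar patients who fail labs before treatment 3 or 4 already have the Day 57 CT and risk only the week-16 scan. Only secondary endpoints are touched. This is a worthwhile, inexpensive clarification.

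**What to change.** - **4.1.2:** make the consequence of failed recovery discontinuation of study treatment instead of removal from the study, for unilobar and bilobar patients. When DEBIRI is stopped does not change.
- **Add a rule** for any patient who stops DEBIRI before Day 57 for a reason other than treated-lobe progression or withdrawal of consent. This also covers stops for toxicity, intercurrent illness or palliative radiation, which raise the same question. The patient still has the planned week-8 imaging, by CT or by liver MRI as footnote f allows (for example with raised creatinine), and the follow-up scan that 8.0 already requires. After a response, "confirmatory scans must be obtained at least 4 weeks following the initial documentation of complete or partial response"; after apparent progression, "repeat CT will be done at 12 weeks to exclude the possibility of treatment related transient edema". If other anticancer therapy starts sooner, imaging is done before it starts, and apparent progression on a scan before week 8 is flagged as possibly due to edema.
- **4.0 and 4.5:** state that the bar on other anticancer therapy ends when study treatment is discontinued. Otherwise keeping patients on study for a scan would also prolong the bar.

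Section 9.1.2 needs no edit.

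The cost is a few already-planned scans in patients off treatment. The conditional repeat falls at 57 + 28 = Day 85 or later after a response, or at week 12 (1 + 84 = Day 85) after progression. Day 85 is 17-22 days after the 30-day visit if removal counts as completion (85 − 68 and 85 − 63), and lies within the two-year telephone follow-up. Some early scans will be open to confounding by edema. Contrast risk is handled by the MRI option. Dosing, safety rules and sample size do not change.
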